 - k) History of weight gain/loss $\geq 10\%$ of body weight within 6 months (26 weeks) prior to or during the Screening Period
 - l) Uncontrolled hypertension, as defined by systolic blood pressure (SBP) > 160 and/or diastolic blood pressure (DBP) > 100 during Screening, unless discussed with medical monitor. Blood pressure may be rechecked as clinically indicated
 - m) QT interval corrected using Fridericia's formula (QTcF) > 480 msec on 12-lead ECG during Screening, confirmed by repeat ECG 30-60 minutes after the initial ECG
 - n) Any acute or chronic cardiovascular condition (e.g., ischemic heart disease, congestive heart failure) considered clinically significant by the investigator
 - o) Known immunocompromised status, including but not limited to, individuals who have undergone organ transplantation, who are known to be positive for human immunodeficiency virus, or who have recurrent or chronic systemic bacterial, fungal, viral or protozoal infections
 - p) Major episode of infection requiring hospitalization within 4 weeks prior to or during the Screening Period
 - q) Inability to tolerate SC medication
 - r) Inability to tolerate venipuncture
 - s) Women who are breastfeeding
4. Prior and concomitant therapy
- a) Participants who have taken systemic corticosteroids at a dose exceeding 20 mg/day prednisone or equivalent for more than 7 consecutive days at any time within 3 months (12 weeks) prior to or during the Screening Period
 - b) Inability to comply with restrictions and prohibited treatments
 - c) Prior exposure to BMS-986036 or other FGF21 analogs
 - d) Other investigational agents must be discontinued at least 4 weeks or 5 half-lives before the first dose of study medication, whichever is longer
5. Physical and laboratory test findings
- a) Evidence of organ dysfunction or any clinically significant deviation from normal in physical examination, vital signs, or clinical laboratory determinations beyond what is consistent with the target population
 - b) ALT value $> 5 \times$ the upper limit of normal (ULN) as defined by the central laboratory
 - c) AST value $> 5 \times$ ULN as defined by the central laboratory
 - d) Total bilirubin > 1.5 mg/dL (unless the participant has a documented diagnosis of Gilbert's syndrome)
 - e) Serum albumin < 3.5 g/ dL
 - f) Platelet count $< 100 \times 10^3/\mu\text{L}$
 - g) International normalized ratio (INR) > 1.4 , unless due to therapeutic anticoagulation

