- h) Fasting plasma glucose < 60 mg/dL (< 3.33 mmol/L) or > 350 mg/dL (> 19.43 mmol/L)
 - i) Hemoglobin A1c \geq 10%
 - j) Fasting TGs > 500 mg/dL
 - k) Estimated Glomerular filtration rate (eGFR) < 30 mL/min/1.73 m² according to the Modification of Diet in Renal Disease equation
 - l) Evidence of significant worsening of ALT, AST or bilirubin during the Screening Period, in the opinion of the investigator or medical monitor
 - m) A centrally read DXA BMD T-Score of -2.5 or less at the femoral neck, total hip, or lumbar spine during Screening (exclusionary only if participant is 40 years of age or older)
6. Allergies and adverse drug reactions
- a) History of allergy to FGF21, PEG, or related compounds
 - b) History of drug-induced liver injury (DILI)
7. Other exclusion criteria
- a) Prisoners or participants who are involuntarily incarcerated. **Note:** Under certain specific circumstances, a person who has been imprisoned may be included or permitted to continue as a participant. Strict conditions apply, and sponsor approval is required
 - b) Participants who are compulsorily detained for treatment of either a psychiatric or physical (e.g., infectious disease) illness
 - c) Any factor that, in the opinion of the investigator, would jeopardize the evaluation or safety of the participant or be associated with poor adherence to the protocol
 - d) Participants who are incapable of completing study-related assessments (i.e., participant questionnaires) as they MUST be completed by the participant

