4.3.5 Clinical Laboratory Parameters

- Absolute and change from baseline values at each visit through Week 52/PTFU
- Potential hepatotoxicity by time point
 - Aspartate aminotransferase (AST) or alanine aminotransferase (ALT) > 3 x upper limit of normal (ULN) or > 5 x ULN
 - Total Bilirubin > 2 x ULN
 - (AST or ALT) >3 x ULN and Total Bilirubin > 2 x ULN

Sponsor: Bristol-Myers Squibb

Protocol no: MB130-068

- Post-baseline abnormalities defined by the below categories:
 - Serum albumin < 2.8 g/dL
 - Platelet count < 75 x 10³/ µL
 - Fasting plasma glucose <60 mg/dL or >350 mg/dL
 - Fasting triglycerides > 500 mg/dL
 - Estimated glomerular filtration rate (eGFR) < 30 mL/min/1.73 m²

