6.2.4 Clinical Laboratory Parameters

Based on the safety population, continuous laboratory results will be summarized by visit, treatment group, and pooled BMS-986036. Categorical results such as those for urinalysis will be summarized by number and percentage of participants in each category. These summaries will be based on central laboratory results, except in rare circumstances in which only a local lab value is available then a local lab value may be used. This value will be presented in the same unit and summarized with the central results from other participants. Summaries will present both actual and change-from-baseline results for continuous values.

Sponsor: Bristol-Myers Squibb

Protocol no: MB130-068

The participants with abnormal post-baseline values of laboratory parameters (with available threshold values) will be descriptively summarized by counts and percentages by time point.

Laboratory values below the lower limit or above the upper limit of quantification will be imputed to the lower or upper limit, respectively, for summary tables. The actual values will be displayed in the listings.

Box plots will be presented by time point. All laboratory data specified in the summary tables will be present in listings.

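### The ALT/AST > 3x ULN count in SAP 4.3.5 pools participants already above 3x ULN before dosing with new on-treatment cases, because eligibility admits values up to 5x ULN

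*SAP*

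**What the plan says.** SAP 4.3.5 heads its liver block "Potential hepatotoxicity by time point". The block has an aminotransferase row, "Aspartate aminotransferase (AST) or alanine aminotransferase (ALT) > 3 x upper limit of normal (ULN) or > 5 x ULN", a total bilirubin > 2x ULN row, and a combined row, "AST or ALT) >3 x ULN and Total Bilirubin > 2 x ULN". All are absolute multiples of ULN. SAP 6.2.4 gives the method: "participants with abnormal post-baseline values of laboratory parameters (with available threshold values) will be descriptively summarized by counts and percentages by time point". Neither section mentions a baseline category, a shift table or a rule for a new case in these rows.

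Protocol 8.3.2, criteria 5(b) and 5(c), excludes ALT or AST more than five times "the upper limit of normal (ULN) as defined by the central laboratory". Criterion 5(d) excludes "Total bilirubin > 1.5 mg/dL (unless the participant has a documented diagnosis of" Gilbert's syndrome). Criterion 5(l) excludes "Evidence of significant worsening of ALT, AST or bilirubin during the Screening Period, in the opinion of the investigator or medical monitor"; a stable elevation is not caught by it.

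Protocol 8.5.3.1 treats participants with normal and with elevated Baseline aminotransferases separately when it sets retest triggers, and its stopping rules use multiples of Baseline.

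**The concern.** A table row labelled as potential hepatotoxicity is normally read as something that happened on treatment. Here the threshold lies inside the range that eligibility allows, so some of the people in it may have been there before the first dose.

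Randomization balances these people across arms in expectation, so the row is not biased at entry. After dosing, however, an unsplit count is a net figure: people who enter the row minus people who leave it. Protocol Table 4 predicts dose-related falls in ALT, so departures are expected to be more frequent on active drug. One participant dropping below 3x ULN and another newly rising above it leave the count unchanged. Even if the table has a Baseline column, it shows only totals, not whether those above the line at a later visit are the same people.

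**Working it through.** **1. Compare each SAP 4.3.5 threshold with the entry limit in Protocol 8.3.2.**

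| Parameter | SAP row | Excluded at entry | Can an eligible person already be in the row? |
|---|---|---|---|
| ALT/AST | > 3x ULN | > 5x ULN | Yes, from above 3x to 5x ULN |
| ALT/AST | > 5x ULN | > 5x ULN | No, at the qualifying test |
| Total bilirubin | > 2x ULN | > 1.5 mg/dL, unless Gilbert's | Essentially only through Gilbert's (step 5) |
| Albumin | < 2.8 g/dL | < 3.5 g/dL | No |
| Platelets (10³/µL) | < 75 | < 100 | No |
| Fasting glucose (mg/dL) | < 60 or > 350 | Same | No |
| Fasting triglycerides | > 500 mg/dL | Same | No |
| eGFR (mL/min/1.73 m²) | < 30 | Same | No |

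ALT/AST > 3x ULN is the one row whose threshold falls inside the ordinary eligible range.

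**2. Compare with how the SAP treats baseline elsewhere.** QTcF > 450 msec also lies inside the eligible range (entry excludes a confirmed value > 480 msec), and SAP 4.3.2 and 6.2.3 add categories for increases of > 30 and > 60 msec from baseline. SAP 6.2.6 requires a titer at least 4-fold above baseline before a baseline-positive participant counts as having a drug-induced antibody response. SAP 4.5 gives shifts from baseline for fibrosis and NAS. The liver rows have nothing equivalent.

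**3. How many people could be in the row before dosing?** The documents give no entry share p, so it is assumed to be 2%, 5% or 10%. Arm size is 197/4 = 49.25, taken as 49; one person is 1/49 = 2.0%.

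| | p = 2% | p = 5% | p = 10% |
|---|---|---|---|
| Whole trial, 197p | 3.9 | 9.9 | 19.7 |
| Per arm, 49p | 1.0 | 2.5 | 4.9 |
| At least one in a given arm, 1 − (1 − p)^49 | 63% | 92% | 99% |
| One named active arm starts at least 2 above placebo | 13% | 24% | 30% |
| Any of the three active arms does so | 31% | 47% | 55% |

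The last two lines take independent Binomial(49, p) counts. With f the probability of k cases on placebo and F the probability of at most k + 1 on an active arm, they are 1 − Σ f·F and 1 − Σ f·F³.

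**4. How many might leave the row on active drug?** Protocol Table 4 predicts ALT changes of −16.7%, −22.6% and −26.7% for 10, 20 and 40 mg. The highest entry ALT that would fall to 3x ULN is 3/(1 − fall). If entry values were spread evenly over 3x to 5x ULN (an assumption), the share leaving is (that value − 3)/2.

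| | 10 mg | 20 mg | 40 mg |
|---|---|---|---|
| Entry ALT falling to 3x ULN | 3/0.833 = 3.60x | 3/0.774 = 3.88x | 3/0.733 = 4.09x |
| Share leaving | 30% | 44% | 55% |
| People per arm, p = 5% | 0.7 | 1.1 | 1.3 |
| People per arm, p = 2% to 10% | 0.3 to 1.5 | 0.4 to 2.1 | 0.5 to 2.7 |

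Table 4 is for a typical participant and covers ALT only. A raised AST alone can keep someone in the row, and no placebo change is given.

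**5. Bilirubin at entry.** The 1.5 mg/dL cap is at or below 2x ULN for any ULN of at least 1.5/2 = 0.75 mg/dL. The ULN is not in the documents; at an assumed 1.0 to 1.3 mg/dL the cap is 1.50x to 1.15x ULN.

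**6. Worsening in those already above 3x ULN.** Doubling a value above 3x ULN gives more than 2 × 3 = 6x ULN, which is already in the > 5x row.

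**The case against.** The strongest reply is that this is table layout, which the SAP leaves to shells that are not in the documents (SAP Appendix 2), and the split may already be there. That stands as a limit: the gap is in the SAP text, and the shells could close it.

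A second reply is that the expected ALT fall is reported directly. SAP 4.5 plans ALT and AST change from Baseline at every visit through Week 52 and normalization at Weeks 24 and 48. SAP 6.4 adds covariance and repeated-measures models for exploratory endpoints. SAP 6.2.4 adds box plots and listings. Potential drug-induced liver injury is reported as an SAE (Protocol Appendix 8) and shown graphically (SAP 6.2.1). All true, and it lowers the importance. But the summaries and models describe groups, listings need tracing by hand, and the drug-induced injury definition also requires raised bilirubin, so it does not cover an isolated ALT/AST rise. None shows in the planned table who is newly above 3x ULN.

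A third reply is that the magnitudes stack assumptions: no source for the entry share, an even spread over 3x to 5x ULN, and a typical-participant prediction applied to the upper tail. That is also right. The figures show only what is plausible.

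A reader might go further and infer that the bilirubin and combined rows are mixed to the same degree. The documents do not support this. Entry above the bilirubin line essentially needs the Gilbert's exception, a combined case needs raised ALT/AST as well, and the number may be zero. Criterion 5(a), which excludes clinically significant deviations in "clinical laboratory determinations beyond what is consistent with the target population", narrows it further at the investigator's discretion.

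**Conclusion.** The point holds for the ALT/AST > 3x ULN row, as a minor reporting improvement. On the SAP text, that row counts people above the line before dosing together with new cases, and it nets departures against arrivals. The size is unknown. Under an assumed entry share of 2% to 10%, about 1 to 5 people per arm would start in the row, and roughly 0.3 to 2.7 per active arm might leave it if ALT fell as Table 4 predicts. No efficacy analysis is affected.

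Three stronger readings should be resisted. First, a hepatic signal is not lost: the individual data are collected and listed, and absolute counts are reported. Second, a separate flag for doubling of Baseline is not needed for those above 3x ULN at entry, since doubling puts them in the > 5x row. That row is largely free of entry cases, although the exclusion applies to the last result before randomization, so a Day 1 value could still differ. Third, the SAP does not leave Baseline open. SAP 8.1 fixes it as the last pre-dose measurement unless stated otherwise, and 4.3.5 states nothing else. The Screening and Day 1 mean in Protocol 8.5.3.1 is confined to evaluating potential drug-induced liver injury.

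**What to change.** In SAP 4.3.5 and 6.2.4, keep every absolute count. For the ALT/AST > 3x ULN row, also report by arm and time point:

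- participants already above 3x ULN at Baseline, using the SAP 8.1 definition;
- new post-baseline cases, with a missing Baseline counted as new.

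A shift table by baseline category would serve equally well. Keep the > 5x ULN row as it is. For any participant in the bilirubin or combined row, show Baseline values and Gilbert's status in the listing; no further split of those rows is needed.

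All of this uses data already collected. The cost is some SAP wording, a little programming and a slightly longer table. If the table shells already contain the split, one sentence in the SAP is enough.

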4.3.6 Bone Mineral Density Testing (BMD)

BMD as measured by DXA at Week 48 (or ET, if applicable), and 6 months (1 month is defined as 4 calendar weeks) after the Week 52/PTFU Visit, following will be summarized.

- Absolute and change from baseline values

4.3.7 Immunogenicity

- Proportion of participants with anti-BMS-986036 antibodies (including neutralizing) through Week 52/PTFU and in long-term follow-up
- Proportion of participants with anti-FGF21 antibodies (including neutralizing) through Week 52/PTFU and in long-term follow-up

4.4 Pharmacokinetic Endpoints

- Trough (predose) BMS-986036 concentrations from samples collected at each visit

4.5 Exploratory Endpoints

Exploratory endpoints include the following:

- Quantitative measurements of fibrosis and fat on biopsy
 - Assessment of NASH CRN Fibrosis Score at Week 24
 - Proportion of participants with >=2 stage improvement
 - Changes in Fibrosis (as expressed by Shift from baseline)
 - Proportion of participants with >=1 stage improvement, no change, or worsening
 - Assessment of Ishak Fibrosis Score at Week 24
 - Proportion of participants with >=2 stage improvement
 - Changes in Fibrosis (as expressed by Shift from baseline)
 - Proportion of participants with >=1 stage improvement, no change, or worsening
 - Assessment of Fibrosis and NASH using digital pathology at Week 24
 - Absolute, percent change, and change from baseline
 - Assessment of CPA at Week 24
 - Proportion of participants with any improvement
 - Absolute, percent change, and change from baseline
 - Assessment of fat in stained tissue by morphometry and alpha smooth muscle actin (SMA) at Week 24
 - Absolute, percent change, and change from baseline
- Assessment of NAS score at Week 24
 - Changes in NAS (as expressed by shift from baseline, for each individual NAS components (Steatosis, inflammation, Ballooning) as well as Total score)

Sponsor: Bristol-Myers Squibb

[figure not shown]
Protocol no: MB130-068

- Proportion of participants with improvement, no change, or worsening in NAS Total
- Assessment of NASH using digital pathology
 - Absolute, percent change, and change from baseline
- Hepatic fat fraction as measured using MRI-PDFF at Week 24 and Week 48
 - Absolute, percent change, and change from baseline
 - Proportion of subjects in each treatment group with $\geq 30\%$ relative reduction, $\geq 20\%$ relative reduction, $\geq 10\%$ relative reduction, and $\geq 5\%$ absolute reduction
- Noninvasive measures of fibrosis and/or cirrhosis
 - Liver stiffness as determined by Magnetic Resonance Elastography (MRE) at Week 24 and Week 48
 - Absolute, percent change, and change from baseline
 - Proportion of subjects in each treatment group with $\geq 19\%$ or $\geq 15\%$ reduction
- Noninvasive scores of hepatic fibrosis (AST-Platelet Ratio Index (APRI), Fibrosis 4 (FIB-4), Enhanced Liver Fibrosis (ELF), and NAFLD Fibrosis Score) from Day 1 to Week 24 and Week 48
 - Absolute, percent change, and change from baseline
 - Proportion of participants in each ELF category by time point
- Metabolic assessments at Week 24 and Week 48
 - Physical assessments (body weight, waist circumference, and body mass index (BMI)) by time point
 - Serum lipids (low-density lipoprotein (LDL), high-density lipoprotein (HDL), and triglycerides (TGs))
 - Absolute and change from baseline
 - Abnormal post-baseline values according to thresholds identified in SAP Section 4.3.5
 - Plasma glucose, Plasma insulin, Hemoglobin A1c
 - Absolute and change from baseline
 - Abnormal post-baseline values according to thresholds identified in SAP Section 4.3.5
- Patient-reported outcomes at Week 24 and Week 48
 - 3-Level EuroQol of Life 5 Dimension (EQ-5D-3L) Questionnaire
 - Absolute and change from baseline in visual analog score and utility index
 - Proportion of participants in each 3-level dimension by time point
 - 36-Question Short Form Quality-of-Life (SF-36) Questionnaire
 - Absolute and change from baseline in continuous variables defined in SAP Section 8.0
 - Chronic Liver Disease Questionnaire-Nonalcoholic Fatty Liver Disease (CDLQ-NAFLD)
 - Absolute and change from baseline in continuous variables defined in SAP Section 8.0
- Exploratory biomarkers
 - Transaminases
 - ALT normalization ($ALT \leq ULN$) at Week 24 and Week 48
 - AST normalization ($AST \leq ULN$) at Week 24 and Week 48
 - ALT at each visit through Week 52/PTFU
 - AST at each visit through Week 52/PTFU
 - Change from Baseline (Day 1 predose) ALT levels at each visit through Week 52/PTFU Visit
 - Change from Baseline (Day 1 predose) AST levels at each visit through Week 52/PTFU Visit.
 - PRO-C3 (N-terminal type 3 collagen propeptide)

[figure not shown]
Sponsor: Bristol-Myers Squibb

Protocol no: MB130-068

- Assessment of PRO-C3 levels at each visit through Week 52/PTFU
- Change from Baseline (Day 1 predose) in PRO-C3 levels at each visit through Week 52/PTFU Visit

- Assessment of adiponectin at each visit through Week 52/PTFU
 - Absolute, percent change, and change from baseline

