8.3.1 Inclusion Criteria

1. Signed written informed consent
 - a) Participants must be willing to participate in the study and sign the informed consent form(s) (ICF[s])
 - b) Participants (and caregivers as applicable) must be willing and able to complete all study-specific procedures and visits
2. Liver biopsy performed within 6 months (26 weeks) prior to the Screening Period. Biopsy performed prior to ICF must be available to the central reader prior to randomization. If historical biopsy is not available, a liver biopsy will be performed during the Screening Period (see [Section 8.5.1.1](#)). Biopsy must be consistent with NASH, with:
 - a) A score of at least 1 for each NAS component (steatosis, lobular inflammation, and ballooning), as assessed by the central reader
AND
 - b) Stage 3 liver fibrosis according to the NASH CRN classification, as assessed by the central reader
3. Participants taking anti-diabetic, anti-obesity, or anti-dyslipidemic medications must have been on stable regimens for at least 3 months (12 weeks) (6 weeks for statins) prior to and during the Screening Period. The investigator may contact the medical monitor regarding the stability of a participant's regimen when determining eligibility for study participation. Participants taking vitamin E at doses ≥ 800 IU/day must have been on stable doses for at least 6 months (26 weeks) prior to and during the Screening Period. Vitamin E treatment (≥ 800 IU/day) must not have been initiated after the qualifying liver biopsy was performed.

4. Age and reproductive status
 - a) Men or women 18 to 75 (inclusive) years of age
 - b) Women of childbearing potential (WOCBP) must have a negative pregnancy test (minimum sensitivity 25 IU/L or equivalent units of human chorionic gonadotropin) within 24 hours prior to the start of study medication
 - c) Women must not be breastfeeding at any time during the study
 - d) WOCBPs must agree to follow instructions for method(s) of contraception for the duration of treatment (BMS-986036 or placebo) plus 5 half-lives of study medication (5 days) plus 30 days (duration of ovulatory cycle) for a total of 35 days after the end of the Double-Blind Treatment Period
 - e) WOCBPs who are continuously not heterosexually active are exempt from contraceptive requirements but must undergo pregnancy testing as described in the Schedule of Activities in [Section 1](#)

[figure not shown]

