8.5.1.2 Noninvasive Scores of Hepatic Fibrosis

The ELF, FIB4, APRI, and NAFLD Fibrosis Score are composite indices that have been correlated with fibrosis stage in NASH study participants.²³

ELF assay, FIB4, APRI, and NAFLD Fibrosis Score use a variety of algorithms combining a number of physical attributes and biochemical and hematologic test values to determine the level of the participant's liver fibrosis (see [Appendix 9](#)). The scores will be calculated by a computerized system based on laboratory values and nonlaboratory parameters entered into the eCRF by personnel at the site. The sites will not be required to calculate scores.

Details on the collection, processing, and shipping of samples for fibrosis scoring are in the Central Pathology Manual.

- ELF assessment combines hyaluronic acid, procollagen 3 amino terminal peptide, and TIMP-1. A proprietary algorithm is used to evaluate each of these markers by immunoassay, to create an ELF Score
- FIB4 scores fibrosis by combining participant age, ALT, AST, and platelet count. The formula used to calculate the FIB4 score is provided in [Appendix 9](#)
- APRI scores fibrosis by combining AST and platelet count. The formula used to calculate the APRI Score is provided in [Appendix 9](#)
- The NAFLD Fibrosis Score scores fibrosis by combining participant age, BMI, fasting glucose, presence of diabetes, ALT, AST, platelet count, and albumin. The formula used to calculate the NAFLD Fibrosis Score is provided in [Appendix 9](#)

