8.0 Conventions and General Definitions

8.1 General Definitions

Term	Definition
Study Day	Study day is calculated as: assessment date – date of first dose + 1
Baseline	Unless otherwise stated, Baseline is defined as the last measurement prior to dosing on Day 1 (Week 0). If the measurement on Day 1 is missing or not available, then a prior measurement during the screening period may be used as baseline.
Change from Baseline	Change = Value at post-baseline visit – value at baseline
Change in the maximum post-baseline value	Change = Highest observed value post-baseline – value at baseline
Percent Change from Baseline	Percent change from baseline is defined as ([value at post-baseline visit – value at baseline]/value at baseline) x 100. If the baseline value is 0 and the post-baseline value is also 0, then the percent change from baseline is set to 0.
Study Treatment	For the purposes of the calculations included in this SAP, study treatment will include only doses of BMS-986036 (dose levels of 10 mg QW, 20 mg QW or 40 mg QW) or placebo QW.
Duration of Study Treatment	Duration of study treatment in weeks will be defined as: (date of last dose of study treatment – date of first dose of study treatment+7)/7.
Treatment Completion (%)	Treatment completion (%) will be calculated as the total number of treatment doses received divided by the total number of expected doses (48), multiplied by 100.
End of Study (EOS) Date	The EOS date is the date recorded on the eCRF that a participant either discontinued or completed the study. If the participant is lost to follow-up, the EOS date will be the date of the last visit assessment obtained.
First Dose Date – Study	The date a participant received their first dose as recorded in the eCRF as date study treatment was administered.
Last Dose Date – Study	The date of last recorded dose on the eCRF for a subject.
Unscheduled assessments	Unscheduled measurements will be included in the listings. With the exception of unscheduled measurements used for baseline and unscheduled measurements will be excluded from the descriptive statistics and statistical analysis.

Sponsor: Bristol-Myers Squibb

Protocol no: MB130-068

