8.10 Other Calculations

- ELF assessment combines hyaluronic acid, procollagen 3 amino terminal peptide, and TIMP-1 (tissue inhibitor of metalloproteinases 1). A proprietary algorithm is used to evaluate each of these markers by immunoassay, to create an ELF Score which is provided by an external vendor.
- FIB4 Score = (age [years] × AST level [U/L]) / (platelet count [$\times 10^9/L$] × square root of ALT [U/L]).
- APRI Score = ([AST divided by AST Upper Limit of Normal]/platelet count [$\times 10^9/L$]) × 100
- NAFLD Fibrosis Score = $-1.675 + (0.037 \times \text{age [years]} + (0.094 \times \text{BMI [(kg/m}^2\text{)]}) + (1.13 \times \text{Impaired Fasting Glucose or diabetes [yes = 1, no = 0]}) + (0.99 \times \text{AST/ALT ratio}) - (0.013 \times \text{platelet count [x 10}^9\text{/L}] - (0.66 \times \text{albumin [g/dL]})$). Note, the status of impaired fasting glucose or diabetes (yes or no) will be assessed only once at baseline as recorded by the site in the Specific Disease History eCRF page. This value will be used for all subsequent calculations.

Note for FIB4, APRI, and NAFLD Fibrosis scores that if any one component is missing at a given time point, another non-missing value within an absolute range of 3 days may be used. If there is more than one value that is within 3 days, the closest value after the visit date will be selected. Otherwise, if all components are not available the score will not be calculated at that time point.

Sponsor: Bristol-Myers Squibb

Protocol no: MB130-068

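### Percent change from baseline is planned for the NAFLD Fibrosis Score, which crosses zero, so every participant with a negative baseline who improves is reported as an increase

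*SAP*

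**What the plan says.** SAP 4.5 (Exploratory Endpoints) lists APRI, FIB-4, ELF and the NAFLD Fibrosis Score in a single bullet that ends "Enhanced Liver Fibrosis (ELF), and NAFLD Fibrosis Score) from Day 1 to Week 24 and Week 48". The summaries listed beneath it are "Absolute, percent change, and change from baseline". No score is exempted.

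SAP 8.1 (General Definitions) gives the rule: "Percent change from baseline is defined as ([value at post-baseline visit – value at baseline]/value at baseline) x 100". The denominator is the signed baseline, not its absolute value. There is one special case: "If the baseline value is 0 and the post-baseline value is also 0, then the percent change from baseline is set to 0". Nothing covers a negative baseline, a baseline close to zero, or a zero baseline followed by a non-zero value.

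SAP 8.10 and Protocol Appendix 9 define the score as a linear combination with a negative intercept and two subtracted terms. Protocol 8.5.1.2 says that the noninvasive scores are used "to determine the level of the participant's liver fibrosis", so a lower value is read here as improvement. The documents do not state that direction outright.

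**The concern.** Percent change is interpretable only for a quantity that stays on one side of zero and for which zero means none of it. The NAFLD Fibrosis Score meets neither condition. Two things go wrong:

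- **Sign.** With a negative baseline, improvement is shown as an increase and worsening as a decrease. With a positive baseline the signs are as expected. One column then carries both conventions.
- **Size.** As the baseline approaches zero the ratio grows without limit, so a few participants can dominate the arm mean, SD and range.

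The mean percent change by arm then has no usable meaning, and it can point the opposite way to the absolute change reported beside it. Protocol 6.2.1 bases Phase 3 design and dose selection on the totality of this study's efficacy, safety and PK analyses (together with those of the companion cirrhosis study), so a column that may contradict its neighbour should not be in that package.

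**Working it through.** The plan states no figure on this point, so there is none to reproduce. The check applies the SAP's own two formulas.

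**Formulas**

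- Score (SAP 8.10) = -1.675 + 0.037 × age + 0.094 × BMI + 1.13 × (impaired fasting glucose or diabetes, 1/0) + 0.99 × AST/ALT - 0.013 × platelets - 0.66 × albumin
- Percent change (SAP 8.1) = 100 × (post - baseline) / baseline

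**Step 1: does the score cross zero in eligible participants?** The component values below are assumptions. They respect the age, platelet and albumin limits in Protocol 8.3.1 and 8.3.2.

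| Age | BMI | Diabetes | AST/ALT | Platelets | Albumin | Score |
|---|---|---|---|---|---|---|
| 50 | 32 | no | 0.8 | 220 | 4.4 | -1.79 |
| 50 | 32 | yes | 0.8 | 220 | 4.4 | -0.66 |
| 57 | 34 | yes | 50/65 | 220 | 4.3 | -0.18 |
| 65 | 38 | yes | 1.1 | 150 | 4.0 | +1.93 |

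Third row in full: -1.675 + 2.109 + 3.196 + 1.13 + 0.762 - 2.86 - 2.838 = -0.176.

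**Step 2: sign.** If the baseline is below zero and the post-baseline value is lower still, numerator and denominator are both negative and the quotient is positive. This holds for every such participant and needs no data.

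**Step 3: the same 0.5-point improvement from different baselines**

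| Baseline | Post | Change | Percent change (SAP 8.1) |
|---|---|---|---|
| +1.00 | +0.50 | -0.5 | -50% |
| +0.10 | -0.40 | -0.5 | -500% |
| +0.05 | -0.45 | -0.5 | -1000% |
| -0.05 | -0.55 | -0.5 | +1000% |
| -0.176 | -0.676 | -0.5 | +283% |
| -0.35 | -0.85 | -0.5 | +143% |
| -1.00 | -1.50 | -0.5 | +50% |

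A worsening from -1.0 to -0.5 prints as -50%, identical to a true improvement from +1.0 to +0.5.

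**Step 4: how many participants are affected?** The documents give no baseline distribution. I simulated three assumed covariate mixes, each with SDs of 10 years, 6 kg/m², 0.3 (AST/ALT), 60 (platelets) and 0.3 g/dL (albumin), truncated at the age, platelet and albumin limits:

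| Mean age | Mean BMI | Diabetes | Mean AST/ALT | Mean platelets | Mean albumin | Score mean (SD) | Share below 0 |
|---|---|---|---|---|---|---|---|
| 60 | 37 | 80% | 1.0 | 190 | 4.2 | 0.64 (1.14) | 28% |
| 57 | 35 | 70% | 0.85 | 210 | 4.4 | -0.29 (1.19) | 59% |
| 52 | 32 | 50% | 0.8 | 230 | 4.5 | -1.34 (1.22) | 86% |

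**Step 5: effect on the arm mean.** The setting is 5,000 simulated arms of 49 participants, with baseline normal and SD 1.2, and every participant improving by exactly 0.3. The true change is -0.3 in every arm.

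| Baseline mean | Arms whose mean percent change is positive | Central 95% of arm means |
|---|---|---|
| +0.5 | 39% | -323% to +313% |
| 0 | 50% | -404% to +414% |
| -0.5 | 61% | -353% to +413% |

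With uniform improvement in every participant, whether the arm mean shows improvement or worsening is close to a coin toss.

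**The case against.** The best defence concerns reach. This is one of three descriptive summaries of one of four scores within an exploratory endpoint. Absolute value and change from baseline are planned beside it. The ANCOVA and repeated-measures models in SAP 6.4 use change from baseline. Responder cut-offs based on relative reduction are set for MRI-PDFF and MRE, not for this score. Primary and secondary endpoints, power and alpha are untouched. All of this stands and limits the seriousness.

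Three further points stand in part:

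- **Robust summaries.** The SAP also plans medians (6.4, 6.5) and quartiles (6.5), which resist the explosion near zero. They do not cure the sign reversal.
- **Size of the example.** Diabetes status is fixed at baseline and age barely moves. A 0.5-point fall from a single component would need about 38 × 10⁹/L more platelets (0.5/0.013), a BMI loss of about 5.3 (0.5/0.094), an albumin rise of about 0.76 g/dL (0.5/0.66) or an AST/ALT fall of about 0.5 (0.5/0.99). A 0.1-point fall from -0.176 prints as +57%: less dramatic, still the wrong sign.
- **Frequency.** The share of negative baselines is not in the documents, and the 28% to 86% range rests on assumptions.

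The table shells are separate documents, so the final output cannot be seen. That does not correct the rule written in the SAP.

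**Conclusion.** The concern holds. As written, SAP 4.5, 8.1 and 8.10 together produce a percent change with the wrong sign for every participant who starts below zero and improves, or who starts below zero and worsens. The value is unstable for anyone who starts near zero. The sign reversal is algebra. It depends on no assumption beyond reading a fall in the score as improvement.

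The size in this trial depends on the baseline distribution. Under the assumed mixes, between about a quarter and most of the participants would be affected. APRI and FIB-4 are ratios of positive quantities and are not affected. The ELF algorithm is proprietary, so its range cannot be checked from the documents. The consequence is a misleading exploratory column; no confirmatory conclusion is damaged. It should be corrected because the planned statistic is invalid and the correction costs almost nothing.

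**What to change.** In SAP 4.5, remove percent change for the NAFLD Fibrosis Score and report absolute value and change from baseline only. A 0.5-point improvement then reads -0.5 whatever the baseline. The SAP already follows this pattern for lipids, glucose, insulin, hemoglobin A1c and the patient-reported outcomes.

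Keep percent change for APRI and FIB-4. For ELF, confirm with the vendor that the score stays positive before keeping it. Make sure that the sentence in SAP 6.4 adding percent change for other biomarkers is not read as restoring it for this score.

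Dividing by the absolute baseline is not an adequate alternative. It corrects the sign (-1.0 to -1.5 becomes -50%) but not the instability (-0.05 to -0.55 still gives -1000%).

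The cost is one line in SAP 4.5 and one fewer table column. Protocol 9.4.4 lists these scores without asking for percent change, so no protocol amendment is needed on this point.
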